#### 12.2.8 Minimal residual disease assessment

Absence of evidence of clonal myeloma population based on multichannel flow cytometry with discrimination of 1:1x10^4 – 1x10^5

### 13. DATA REPORTING / REGULATORY REQUIREMENTS

Adverse event lists, guidelines, and instructions for AE reporting can be found in Section 7.0 (Adverse Events: List and Reporting Requirements).

#### 13.1 Data Reporting

##### 13.1.1 Method

The Office of Data Quality (ODQ) will collect, manage, and perform quality checks on the data for this study.

##### 13.1.2 Responsibility for Data Submission

Investigative sites within DF/HCC or DF/PCC are responsible for submitting data and/or data forms to the Office of Data Quality (ODQ) in accordance with DF/HCC policies.

#### 13.2 Data Safety Monitoring

The DF/HCC Data and Safety Monitoring Committee (DSMC) will review and monitor toxicity and accrual data from this study. The committee is composed of medical oncologists, research nurses, pharmacists and biostatisticians with direct experience in cancer clinical research. Information that raises any questions about participant safety will be addressed with the Overall PI and study team.

The DSMC will review each protocol up to four times a year with the frequency determined by the outcome of previous reviews. Information to be provided to the committee may include: up-to-date participant accrual; current dose level information; TLT information; all grade 2 or higher unexpected adverse events that have been reported; summary of all deaths occurring within 30 days of intervention for Phase I or II protocols; for gene therapy protocols, summary of all deaths while being treated and during active follow-up; any response information; audit results, and a summary provided by the study team. Other information (e.g. scans, laboratory values) will be provided upon request.

### 14. STATISTICAL CONSIDERATIONS

## 14.1 Study Design

The study is designed as a Phase II open label study of vaccination with DC/myeloma fusions/GM-CSF plus nivolumab therapy as part of treatment for patients with relapsed multiple myeloma. Patients meeting initial eligibility will undergo harvesting tumor cells and undergo vaccine production. During this period patients will receive an initial cycle of nivolumab and will then undergo a series of vaccinations on day 1 of cycles 1-3. 25 evaluable patients will be enrolled. Therapy with nivolumab will continue for three additional cycles. Based on a prior phase II study of vaccination of myeloma patients with the DC/MM fusion vaccine approximately 50% patients demonstrated a >10-fold increase in IFNy expression to the baseline. Therefore, the combination of vaccination and nivolumab will be considered promising if the study shows evidence of at least 75% patients with >10-fold increase in IFNy expression, and would not be considered promising if >10-fold increase is observed in 50% or less patients. With total n=25 patients, the combination will be considered promising for further study if 17 or more patients demonstrate significant immune response. This decision rule has a 0.1 (significance level) probability of accepting the combination for further study if the true underlying significant immune response is 50% and a 0.85 (power) probability of accepting the combination if the true underlying immune response is 75%. For the absolute increase in IFNy expression, with n=25 patients, we will have at least 90% power to detect an effect size of 0.66 (one-sided Wilcoxon rank sum test, significant level of 0.05), which corresponds to a 0.36 difference in log10 IFNy fold increase assuming a standard deviation of 0.54 or a 2.3 difference in IFNy expression fold increase assuming a standard deviation of 3.5. We estimate the median fold increase in IFNy expression of vaccination alone be 14 (DFCI trial 04098). Therefore, the fold-change that can be detected in the combination is at least 16.1.

As a secondary clinical endpoint, response will be assessed according to IMWG response criteria. In a prior phase I trial of DC/MM vaccination in patients with relapsed MM, 69% (11/16) patients had disease stabilization. No patients demonstrated disease response (PR, VGPR, or CR). In the present phase II trial, overall response rate per IMWG criteria will be assessed. An exact binomial test with a 10% one-sided significance level will have 82% power to detect the difference between the ORR proportion of 0.15 (null hypothesis) and the alternative ORR proportion of 0.35 when the sample size is 25. An ORR of 35% is considered worthy of further study in a larger trial.

If 3 or more patients experience a TLT, accrual will be suspended.

	True but Unknown Rate of DLT				
	0.10	0.20	0.25	0.30	0.40
Probability of continuation of enrollment ( $\leq 2$ TLT in 10 pts)	0.930	0.678	0.526	0.383	0.167

If the true rate of TLT is 25%, the probability of observing 2 or fewer TLTs within a cohort of 10 patients is 0.526.

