## 2.2 Vaccine Therapy for Multiple Myeloma

Immune therapy has emerged as a leading area of cancer therapeutics due to its potential to recruit multiple effectors that broadly target malignant cells and overcome mechanisms of resistance. Multiple myeloma (MM) is characterized by the loss of critical mediators of immune surveillance, resulting in the suppression of antigen-presenting and effector cell function and the development of an immunologic milieu that fosters disease progression. We have developed a tumor vaccine in which patient-derived myeloma cells are fused with autologous dendritic cells (DCs), such that a broad array of myeloma antigens are presented in the context of DC-mediated costimulation. In diverse tumor models that include MM, vaccination of animals with DC/tumor fusions results in protection from an otherwise lethal challenge of malignant cells and, more significantly, eradication of disease in the setting of advanced metastatic involvement. In a phase I study, 17 patients with advanced myeloma (median of 4 prior regimens) underwent vaccination with DC/MM fusions in conjunction with 4 days of GM-CSF administered at the vaccine site. In this study, MM cells were isolated from bone marrow aspirates and fused with autologous DCs generated from adherent mononuclear cells cultured with GM-CSF, IL-4, and TNF $\alpha$ . Vaccine production was successful in all patients and was well-tolerated without evidence of clinically significant autoimmunity. Vaccination resulted in a mean 10-fold expansion of CD4 and CD8 myeloma-specific T cells, as determined by the percentage of cells expressing IFN $\gamma$  in response to *ex-vivo* exposure to autologous tumor lysate. Similarly, vaccination resulted in the development of myeloma-specific antibody responses as documented by SERAX analysis.

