We hypothesize that patients will demonstrate enhanced myeloma-specific immunity following exposure to vaccine plus nivolumab as compared to the pre-treatment time point. In a prior study, we observed that patients with multiple myeloma exposed to a MM/DC fusion vaccine had a mean log10-fold increase in myeloma-specific CD4+ T cells from pre-mobilization to post-transplant and from pre-mobilization to peak post-vaccination was 3.55 (95% CI 1.58;8.13) and 9.55 (95% CI 5.37;16.98), respectively. The mean log10 fold increase in myeloma-specific CD8+ T cells from pre-mobilization to post-transplant and from pre-mobilization to peak post-vaccination was 4.37 (95% CI 2.40;7.76) and 8.32 (95% CI 4.68;15.14), respectively. Similarly, in an early phase clinical trial of AML patients receiving AML/DC fusion vaccination following a chemotherapy-induced remission, we also observed enhanced leukemia-specific immunity as evidenced by increased circulating lymphocytes targeting leukemia cells.

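### Section 14.1 uses two vaccine-alone benchmarks that fit poorly together, and the exact error of the 17-of-25 rule at the plan's own null is 0.054, not 0.1

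*Combined protocol and SAP*

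**What the plan says.** The trial has one arm. Section 14.1 states that "25 evaluable patients will be enrolled" and that "the combination will be considered promising for further study if 17 or more patients demonstrate significant immune response".

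The null rate is introduced with "Based on a prior phase II study of vaccination of myeloma patients with the DC/MM fusion vaccine", in which "approximately 50% patients demonstrated a >10-fold increase in IFNy expression to the baseline". The target is "at least 75% patients with >10-fold increase in IFNy expression". For 17 of 25, the section gives an error of 0.1 if the true rate is 50% and power of 0.85 if it is 75%.

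The paragraph then turns to fold increase as a continuous measure, with an SD of 0.54 on the log10 scale, and adds: "We estimate the median fold increase in IFNy expression of vaccination alone be 14 (DFCI trial 04098".

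The background sections give further vaccine-alone averages:
- Section 2.2, phase I in advanced myeloma: "Vaccination resulted in a mean 10-fold expansion of CD4 and CD8 myeloma-specific T cells".
- Section 2.3, transplant study, first cohort, pre-mobilization to peak: 10.72 (CD4) and 11.48 (CD8).
- Sections 2.3 and 2.8.1, the same study, all patients: 9.55 (CD4) and 8.32 (CD8). The CD4 sentence in 2.8.1 ends "peak post-vaccination was 3.55 (95% CI 1.58;8.13) and 9.55 (95% CI 5.37;16.98), respectively", where 3.55 is the rise already seen post-transplant.

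**The concern.** With no control arm, the null rate is the whole comparison: a go means only that the observed rate beat what the vaccine is believed to do alone. Section 14.1 gives two versions of that belief. If about half of patients exceed 10-fold, the median is near 10. If the median is 14, at least half of patients reach 14-fold, and anyone between 10 and 14 pushes the share above 10-fold past 50%. The plan does not reconcile the two. It also does not say which patients, which baseline or which of CD4 and CD8 either figure describes, so a reader cannot tell whether they measure the same thing.

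At stake is the meaning of a positive result. If the vaccine-alone rate is higher than 50%, the vaccine with an inert partner would pass 17 of 25 more often than the plan says, and the result could be credited to nivolumab.

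**Working it through.** **Inputs.** From 14.1: n = 25, cut-off 17, null 0.50, alternative 0.75, vaccine-alone median 14, log10 SD 0.54. From 2.3: averages 8.32, 9.55, 10.72 and 11.48.

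**Step 1: the plan's own figures.** Exact binomial, X ~ Bin(25, p).
- P(X ≥ 17 | p = 0.50) = 0.0539. The stated 0.1 is not reproduced.
- P(X ≥ 17 | p = 0.75) = 0.8506. The stated 0.85 is reproduced.
- A cut-off of 16 gives 0.115 and 0.929, so it does not yield 0.1 either. The true size at 17 is 0.054, and 0.1 is correct only as an upper bound.

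**Step 2: what a median of 14 implies for the share above 10-fold.** Without any distribution, the share is at least 50%. To attach a size, assume log-normal folds:

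share = Φ((log10(median) − 1) / SD)

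With median 14, log10(14) = 1.146, so share = Φ(0.146 / 0.54) = Φ(0.271) = 0.607.

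**Step 3: false-go rate, P(X ≥ 17 | 25, share), with no nivolumab effect.** The documents do not tie the SD of 0.54 to trial 04098, so a range is shown.

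| Vaccine-alone centre | SD | Share >10-fold | P(≥17 of 25) |
|---|---|---|---|
| 14 (14.1) | 0.40 | 64.3% | 0.44 |
| 14 (14.1) | 0.54 | 60.7% | 0.30 |
| 14 (14.1) | 0.90 | 56.4% | 0.17 |
| 11.48 (CD8, first cohort) | 0.54 | 54.4% | 0.122 |
| 10.72 (CD4, first cohort) | 0.54 | 52.2% | 0.083 |
| 9.55 (CD4, all patients) | 0.54 | 48.5% | 0.040 |
| 8.32 (CD8, all patients) | 0.54 | 44.1% | 0.014 |

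The last four rows read the averages in 2.3 as back-transformed log means. Their confidence limits fit this: √(5.37 × 16.98) = 9.55.

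**Step 4: how much room the rule has.** Solving P(X ≥ 17 | 25, p) = 0.10 gives p = 0.533. The margin over the null, itself given as approximate, is about three percentage points.

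**Step 5: false-go rate of 17 of 25 by true vaccine-alone rate.**

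| True rate | 45% | 50% | 55% | 60% | 65% |
|---|---|---|---|---|---|
| P(≥17 of 25) | 0.017 | 0.054 | 0.134 | 0.274 | 0.467 |

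**Step 6: if the null were 61%.** At p = 0.607, a cut-off of 18 gives 0.17 and a cut-off of 19 gives 0.08. Error at or below 0.1 therefore needs 19 of 25, and power at 75% is P(X ≥ 19 | 25, 0.75) = 0.56.

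**The case against.** The best defence is that the plan's error statement is conditional on a true rate of 50%. There the actual error is 0.054, so 0.1 is met as a bound. That stands: the figure is imprecise in the safe direction, and a claim that 0.1 is breached at the stated null would be wrong.

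A second defence is that the figures are different summaries (a proportion, a median, back-transformed log means), partly for different subsets. Both 10 and 14 lie inside all four confidence intervals in 2.3 for the peak increase. The first-cohort averages imply 52% and 54%, close to the plan's null, and the phase I mean of 10-fold would also fit 50% if it is a geometric mean, which is not stated. This stands as far as it goes. The benchmarks are not strictly contradictory, and among the averages in 2.3 only the first-cohort CD8 value exceeds 0.10, marginally, at SD 0.54. But 14.1 adopts the median of 14 as its own vaccine-alone estimate, and under the log-normal assumption that value gives a false-go rate above 0.1 at every SD from 0.40 to 0.90.

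A reader might go further and infer that both benchmarks come from transplant patients. The documents do not say so: 14.1 describes neither study's population, and the inference rests only on the transplant study being the one completed myeloma trial of this vaccine described besides the phase I.

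A reader might also divide out the post-transplant rise (3.55 for CD4, 4.37 for CD8) and conclude that the rule is far stricter than stated. That is unsound. Twelve of the 36 patients were vaccinated before transplant, so the rise is not purely a transplant effect, and no SD is given for that contrast.

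**Conclusion.** The point holds in two parts.

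First, and without any distributional assumption, the error of 17 of 25 at a 50% null is 0.054; the plan should not give it as 0.1.

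Second, the vaccine-alone benchmark is not pinned down well enough to fix the false-go rate. Across the plan's own figures at SD 0.54 it runs from about 0.01 to about 0.30, and it passes 0.10 once the true rate exceeds about 53%. The 0.30 depends on log-normal folds and on 0.54 being the right SD for the data behind the median of 14; 0.17 to 0.44 is the fairer statement. That a median of 14 puts at least half of patients above 10-fold needs neither assumption. That the share is clearly above half does depend on the shape.

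The documents do not settle which benchmark is right, or whether the rule is too loose or too strict. They show that, until the null is sourced and reconciled, 17 of 25 cannot be read with a known error rate as evidence that nivolumab adds to the vaccine.

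**What to change.** In 14.1:
1. Name one source for the vaccine-alone benchmark, with its population, baseline time point and T-cell subset.
2. Derive the >10-fold rate and the median fold increase from the same patient-level data in that source, and report both.
3. Restate the null, and the cut-off if the null changes, with exact binomial error and power. If 50% and 17 of 25 are kept, replace 0.1 with 0.054.
4. Add the Step 5 table of false-go rates for nulls of 45% to 65%, so that a result at or near the cut-off can be read against the uncertainty in the benchmark.

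The cost is a re-analysis of earlier trial data and revised wording. The stated error or power may become less favourable: if the null moved to 61%, the 19-of-25 rule in Step 6 would leave power of 0.56 at 75%.

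### The 17-of-25 go rule has an exact type I error of 0.054 at a true rate of 50%, not the stated 0.1; the error is on the conservative side and one sentence corrects it

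*Combined protocol and SAP*

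**What the plan says.** Section 14.1 (Study Design) sets out a single-arm rule. The sample size is fixed: "25 evaluable patients will be enrolled". The null comes from an earlier vaccine study in which "approximately 50% patients demonstrated a >10-fold increase in IFNy expression to the baseline"; the target is 75%. The cut is explicit: "the combination will be considered promising for further study if 17 or more patients demonstrate significant immune response".

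The operating characteristics follow in one sentence. It begins "This decision rule has a 0.1 (significance level) probability of accepting the combination for further study" and continues "if the true underlying significant immune response is 50% and a 0.85 (power) probability of accepting the combination" at a true rate of 75%. Both figures are given as probabilities that this rule accepts the combination.

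The same section gives two other sets of probabilities. The response-rate test is described by its level: "An exact binomial test with a 10% one-sided significance level will have 82% power". The toxicity rule is described by attained probabilities, for example "If the true rate of TLT is 25%, the probability of observing 2 or fewer TLTs within a cohort of 10 patients is 0.526".

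**The concern.** Everything needed to check the sentence is printed beside it: n, the cut, the null rate and the alternative rate. A binomial count is discrete, so the attained type I error of a fixed cut seldom equals a round number such as 0.1. A stated 0.1 next to an attained-looking 0.85 therefore calls for a check.

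At stake is the accuracy of a main operating characteristic. The rule decides whether the combination is called promising, and the false-go probability tells readers how much weight a positive result carries. If 0.1 is wrong, either the cut is not the intended one, which would be a design problem, or only the description is wrong. The check has to separate the two.

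**Working it through.** **Inputs, all from section 14.1.** n = 25; go if X ≥ 17; null p = 0.50; alternative p = 0.75. X is the number of patients with a more than 10-fold increase, one yes/no outcome per patient, so X ~ Binomial(25, p). The rule is one-sided, because only high counts lead to acceptance.

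**Step 1. Stated power.** P(X ≥ 17 | p = 0.75) = Σ C(25,k) 0.75^k 0.25^(25−k) over k = 17 to 25 = 0.8506. The plan's 0.85 is reproduced.

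**Step 2. Stated type I error.** At p = 0.50 every sequence has probability 1/2^25, so the tail is a count of combinations:

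- C(25,17) to C(25,25) = 1,081,575 + 480,700 + 177,100 + 53,130 + 12,650 + 2,300 + 300 + 25 + 1 = 1,807,781
- 2^25 = 33,554,432
- P(X ≥ 17 | p = 0.50) = 1,807,781 / 33,554,432 = 0.0539

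The plan's 0.1 is not reproduced. Ratio: 0.10 / 0.0539 = 1.86.

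**Step 3. Could another cut have been meant?**

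| Go if X ≥ | P(go) at 50% | P(go) at 75% |
|---|---|---|
| 15 | 0.2122 | 0.9703 |
| 16 | 0.1148 | 0.9287 |
| **17** | **0.0539** | **0.8506** |
| 18 | 0.0216 | 0.7265 |
| 19 | 0.0073 | 0.5611 |

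No row gives 0.10 with 0.85. The power matches 17 and neither neighbour, so the cut is as intended and 0.1 is the wrong figure. The smallest cut with type I error at or below 0.10 is 17, which points to the design ceiling as the source of the 0.1.

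**Step 4. Could another method give 0.1?** The normal approximation for X ≥ 17 gives 0.0548 with continuity correction and 0.0359 without. Doubling the exact tail gives 2 × 0.0539 = 0.108, but that is not the probability of accepting the combination, since low counts never lead to acceptance.

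**Step 5. How the rest of the section behaves.** The toxicity table, P(X ≤ 2) with n = 10, computes to 0.930, 0.678, 0.526, 0.383 and 0.167 for true rates of 0.10, 0.20, 0.25, 0.30 and 0.40, as printed, so those are attained values. The response-rate test corresponds to a cut of 7 of 25: exact level 0.070 at 15% and power 0.827 at 35%. There the 10% is worded as the level of the test, which is acceptable for a nominal level.

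**Step 6. Sensitivity to the null rate.** The plan gives the null only approximately. For the same rule:

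| True rate | P(X ≥ 17) |
|---|---|
| 50% | 0.054 |
| 52% | 0.080 |
| 53.3% | 0.10 |
| 54% | 0.114 |
| 55% | 0.134 |
| 60% | 0.274 |

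**The case against.** The strongest reply is that 0.1 is the nominal level. The parenthesis calls it a significance level, the cut of 17 does satisfy a 0.10 ceiling, and the response-rate test in the same section uses a nominal 10% whose exact value is 0.070. This probably explains how the figure arose. It does not make the sentence correct: the sentence says the rule has this probability of accepting the combination, and it pairs the figure with 0.85, which is attained.

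A second reply is rounding: 0.054 is 0.1 to one decimal. But the power in the same sentence has two decimals, and to two decimals the value is 0.05. A reader will take 0.1 as 10%.

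A third reply is that the discrepancy has no consequence and that section 14.1.1 labels the more than 10-fold proportion a secondary analysis. The lack of consequence for conduct is accepted and is why the point is minor. The labelling tempers its importance, but section 14.1 still uses this rule to define promising.

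One part of the opposing case stands as a limit: the error is conservative only near a true rate of 50%. The same section also says "We estimate the median fold increase in IFNy expression of vaccination alone be 14 (DFCI trial 04098". A median of 14-fold on the same measure would put at least half of vaccine-alone patients above 10-fold. As an illustration only, assume log-normal fold increases and the plan's log10 SD of 0.54. Then (log10 14 − 1)/0.54 = 0.146/0.54 = 0.27, so about 61% would exceed 10-fold and the false-go probability would be about 0.30. The plan does not say that the two figures share a study, baseline or T-cell subset, so this is a question for the sponsor and not a second error.

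**Conclusion.** The concern holds, as a minor error. The stated acceptance probability at a true rate of 50% is 0.1; the exact value is 0.054. The stated power of 0.85 is correct (0.851). The cut of 17 and the sample size of 25 are consistent with that power and with a nominal one-sided ceiling of 0.10, so the design calculation stands and only its description is wrong.

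At the stated null the rule is stricter than described, and no go or no-go outcome changes. This rests on 25 evaluable patients, one binary outcome per patient, and a null of exactly 50%. The conservative margin is used up at a true vaccine-alone rate of about 53%.

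**What to change.** Replace the sentence on operating characteristics in section 14.1 with wording such as:

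> Nominal one-sided significance level 0.10. The rule of 17 or more of 25 has an exact type I error of 0.054 if the true response rate is 50% and power of 0.851 if it is 75%.

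As a clarifying query, ask the sponsor to name the study, the baseline time point and the T-cell subset (CD4, CD8, either or both) behind the 50% null, and likewise behind the 14-fold vaccine-alone median. Readers can then judge whether 50% is the right reference for the exact figure.

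Cost: one sentence. Sample size, cut and power are unchanged.

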### 14.1.1 Primary Immunologic Endpoint

Myeloma reactive T-cells: Log transformations will be used to induce normality in quantitative measurements, and if still non-normal, then nonparametric tests will be used. The primary endpoint of log 10 peak change in tumor reactive T cells from baseline will be quantified. A secondary analysis of peak change in tumor reactive T cells will be done by comparing the proportions of patients who experience >10-fold increase in IFNy expression, using a chi-squared test. Peak immune response will be correlated with clinical response in an exploratory fashion to assess the relationship between immune response and clinical response.

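### The stated detectable fold-change of 16.1 treats a ratio as a difference; the plan's own log10 figures give a median of about 32, and power at 16.1 is only 13–14%

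*Combined protocol and SAP*

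**What the plan says.** All the figures are in section 14.1 (Study Design). The trial has a single arm, and "25 evaluable patients will be enrolled". For the continuous immune measure the plan claims "at least 90% power to detect an effect size of 0.66", based on a "one-sided Wilcoxon rank sum test, significant level of 0.05".

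It translates that effect size in two ways, as a 0.36 difference on the log10 scale and as a difference on the fold scale. The wording runs "fold increase assuming a standard deviation of 0.54 or a 2.3 difference in" fold increase, the latter with an SD of 3.5. It puts the median fold increase in IFNγ "expression of vaccination alone be 14 (DFCI trial 04098") and concludes: "Therefore, the fold-change that can be detected in the combination is at least 16.1".

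Two other statements bear on the point. Earlier in the same paragraph, for the prior vaccine study, "approximately 50% patients demonstrated a >10-fold increase in" IFNγ expression. Section 14.1.1 fixes the analysis scale: "The primary endpoint of log 10 peak change in tumor reactive T cells from baseline will be quantified".

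**The concern.** A difference of 0.36 in log10 is a ratio on the original scale, so the two translations of the effect size cannot both be additive statements about the same data. The numbers 2.3 and 3.5 look like the log10 pair antilogged and then relabelled as a difference and an SD.

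If so, the plan's only sensitivity statement for the endpoint that section 14.1.1 calls primary is wrong by a wide margin. It says the trial can pick up a rise in the median from 14 to 16.1. A reader who believed that would take a null result as evidence against even a small gain over vaccine alone.

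**Working it through.** **Inputs (section 14.1):** n = 25; one-sided α = 0.05; power at least 90%; effect size d = 0.66; log10 difference 0.36 with SD 0.54; fold-scale difference 2.3 with SD 3.5; reference median 14; stated detectable value 16.1.

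**1. Reproduce the power claim.** Treat 14 as a fixed reference and use a one-sample test. For the t test, power is the upper tail of a noncentral t with 24 degrees of freedom and noncentrality d√n = 0.66 × 5 = 3.30. This gives 0.941. A simulated signed-rank test with its exact critical value gives 0.93. The log10 pair matches the effect size: 0.36/0.54 = 0.667. The claim of at least 90% power therefore reproduces on the log10 scale as a one-sample calculation.

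**2. Identify 2.3 and 3.5.**
- 10^0.36 = 2.29, which rounds to 2.3
- 10^0.54 = 3.47, which rounds to 3.5

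Both are antilogs of the log10 pair: a ratio of geometric means and a geometric SD. The document gives no other source for either.

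**3. Convert the effect to a detectable median.**

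| Calculation | Result |
|---|---|
| Ratio applied to the reference: 14 × 10^0.36 | 32.1 |
| Stated 2.3 added to the reference: 14 + 2.3 | 16.3 |
| Plan's figure | 16.1 |

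The 16.1 follows from neither. It does appear if the smallest effect with exactly 90% power (t test, d = 0.603) is multiplied by 3.5 and added: 14 + 0.603 × 3.5 = 16.11. That origin is inferred, because the plan does not state this effect size.

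**4. Smallest median with 90% power on the log10 scale.**
- t test: 14 × 10^(0.603 × 0.54) = 14 × 2.115 = 29.6
- Signed-rank, d about 0.62: 30.3

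**5. Power at the stated 16.1.** log10(16.1/14) = log10(1.15) = 0.0607, about one sixth of 0.36. Then d = 0.0607/0.54 = 0.112, and power is 0.136 (t) or 0.130 (signed-rank). At 16.3 the t-test power is still only 0.147.

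**6. Could 3.5 be a genuine arithmetic SD?** Under a normal distribution with mean 14 and SD 3.5, P(fold > 10) = Φ((14 − 10)/3.5) = Φ(1.14) = 0.87. The plan gives about 50% for the prior vaccine study and makes 75% the target for the combination. With a log10 mean of log10(14) = 1.146 and SD 0.54, the same probability is Φ(0.146/0.54) = Φ(0.27) = 0.61. That is not 50% either, but it is much nearer.

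**7. The named test.** The rank sum test compares two samples, and this trial has one arm. Against an assumed 12, 24 or 36 historical patients, simulated rank-sum power at d = 0.66 is about 0.55, 0.72 or 0.79. The 90%-power median would then be about 55, 42 or 38. The claim of at least 90% holds only for the one-sample reading.

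**The case against.** The best defence is that the sentence is introduced as being about the absolute increase, so an additive scale is what the plan declares. If 3.5 really were an arithmetic SD, a difference of 2.1 would be d = 2.1/3.5 = 0.60, with t-test power 0.898, and 16.1 would be about right. The source data for the SDs are not in the document, so the exact slip cannot be proved. The 87% check is also imperfect: any median of 14 puts more than half of patients above 10-fold, and the plan does not say that the 50% and the 14 come from the same data.

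The caution about mechanism stands: how 16.1 arose is inference. The additive reading itself does not survive. Both fold-scale numbers match the antilogs after rounding, the primary endpoint is on log10, and even on the additive reading the stated 2.3 gives 16.3.

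A second objection is that the log10 inputs may themselves be optimistic, so 32 should not be presented as firm. That is fair. The intervals for the prior transplant study in section 2.3 imply log10 SDs of roughly 0.74–0.75 for the whole population (assuming 36 analysed) and 1.04–1.05 for the first cohort (assuming 24). Power for a 0.36 difference would then be about 0.75–0.76 or 0.51. This makes 16.1 less defensible still, and it is why 32 is given here as conditional on 14 and 0.54.

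Third, no decision uses 16.1. Section 14.1.1 says the log10 change will be quantified and sets no threshold against 14. That limits the consequence but does not make the figure right.

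**Conclusion.** The concern holds, with high confidence. The log10 and fold-scale statements in section 14.1 are inconsistent, and the fold-scale conclusion is the wrong one. Given a reference median of 14, a log10 SD of 0.54, n = 25, one-sided 0.05 and a one-sample comparison, the planned effect corresponds to a median of about 32. The 90%-power threshold is about 30, and power at 16.1 is 13–14%. The plan thus overstates its sensitivity: it implies that a 15% improvement is detectable when somewhat more than a doubling is needed.

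This is a wrong stated figure that should be corrected, not a design failure. The 17-of-25 rule does not draw on it (exact binomial: 0.054 at a true rate of 50%, 0.851 at 75%), and neither do the response-rate test or the sample size.

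**What to change.** In section 14.1, delete the clause giving a difference of 2.3 with an SD of 3.5, and delete the 16.1. Replace them with text along these lines: *a log10 difference of 0.36 (SD 0.54), that is, a 2.3-fold ratio; from a reference median of 14 this is a median of about 32*. Make clear that the 32 depends on the assumed 14 and 0.54.

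In the same edit, state which test the power refers to. At least 90% is correct for a one-sample signed-rank comparison with a fixed reference. If a two-sample rank sum test against historical patients is intended, give their number and restate the lower power. That choice is the sponsor's and is separate from the arithmetic.

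The cost is a few lines of text and one decision about the test, with no change to sample size, decision rule or response-rate test. The stated sensitivity becomes less favourable, and more so if the rank sum test is kept.
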